The purpose of the SADL-eM is to serve as a treatment tool during inpatient rehabilitation. Over the first week of admission of each person with SCI in each facility, a research clinical supervisor will recruit study participants based on the study eligibility criteria, obtain consent, and assign each consenting patient to one of the two study groups. They will then provide each participant in the intervention group with a SADL-eM hard copy, and explain the purpose of the manual and how to use it. The manual will be reviewed by the treating occupational therapist and the person with SCI during their treatment sessions. During occupational therapy sessions, the therapist will refer to the relevant chapter of the manual. The therapist will also indicate to the participants which parts of the manual are not relevant to them (based on their gender, driving status, or level of SCI). Participants' queries on the content of the manual will be answered by the treating occupational therapist. The therapist will include the manual in as many SADL-eM educational sessions as required, but not less than three sessions per week with 15 minutes per session. The minimum level of clinical experience of each treating occupational therapist will be two years. Good Arabic language comprehension, and the ability to read and write is mandatory for both therapists and patients. No other special skills or experience are required.

The participants will keep the manual to review after sessions and after discharge from the inpatient rehabilitation setting. For the purposes of the study, blinding and bias reduction, the therapists and the participants in the intervention group must not share any part of the manual or information included with other patients or staff. The research assistant who performs data collection, the clinical supervisor, and occupational therapy team will be invited for informational session prior to data collection in each of the participating settings. The informational session will focus on the study purpose, recruitment, eligibility criteria, use of

the SADL-eM, roles, bias reduction, and blinding. Use of data collection tools will take place in a separate session with the research assistant. The principal researcher will answer all questions of the research team during informational sessions and during the research.

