The researchers will use the same outcome measures all through the study and with both of study arms. Biographical data will be collected by a research assistant once on the participant's admission and consent to participate. ADL data collection from each participant in the study will take place in a face-to-face interview twice (on admission before providing with the educational manual and 6 weeks later) using: (a) Patient-administered SCIM-SR and (b) Research assistant-administered SCIM-III, the Private Religiousness Practices Scale, Organizational Religiousness Short-Form, and the domains of ADL covered by the educational manual including driving and community mobility, personal device care, health management and maintenance, Wudu, and Salat. The data will be used to compare the results and means of both groups, answer the research question, and test the study hypothesis.

Polit, et al. (2001) pointed out that the validity of the experimental study can be threatened by history, selection, and maturation. This study finding's validity will be enhanced by concealing intervention group using a blinded assessor. The bias of sampling and contamination will be

minimized through randomization and assuring freedom of participation and anonymity of participants.

Objective data collected in clinical settings using valid and reliable tools is essential for evaluating the impact of an intervention (Polit, et al., 2001). The validity and reliability of the data collected and results of the study will be improved using standardized measurement tools such as SCIM-III and SCIM-SR.

**Biographical Data Collection Tool:** an English 24-item tool that captures demographic and socioeconomic data including age, gender, marital status, level of education, employment, monthly income, accommodation, diagnosis, and cause and type of SCI. The researchers developed the tool to be used in English version in this study.

**Spinal Cord Independence Measure-Self Reported (SCIM-SR):** a patient-reported 17-item tool that evaluates the ability of a person with SCI to perform specified activities independently, with assistance, or with assistive devices. The tool uses an ordinal scale.

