Research supports the criterion validity of SCIM-SR as compared with SCIM III. Pearson correlation and ICC coefficients of the total and the subscale scores met the quality criterion of being above 0.7. The tool is not available in Arabic (Fekete, et al., 2013). The first author will translate the SCIM-SR to Arabic. The Arabic translation will be piloted in the pilot study.

**Spinal Cord Independence Measure-III (SCIM-III):** a 17-task tool that evaluates the ability of a person with SCI to perform specified activities independently, with assistance, or with assistive devices. It is therapist-reported and requires 30 to 45 minutes to complete by assessment but, the interview requires less time [about 20 minutes] (Fekete, et al., 2013). The SCIM has been evaluated in multiple countries including the Middle East and it appears to be resistant to cross-cultural differences. The SCIM-III is valid for use in clinical practice to evaluate function and plan goals of rehabilitation (Glass, et al., 2009). The tool uses an ordinal scale with total score range between 0-100. A higher score indicates greater ADL performance. The SCIM-III has good reliability: Cronbach's alpha: 0.70-0.78, Kappa co-

efficient: 0.64-0.84. Pearson correlation and ICC coefficients of the total and the subscale scores met the quality criterion of being 0.84-0.94. The tool is not available in Arabic and will be used in its English version (Anderson, et al., 2008). Good English language comprehension, and the ability to read and write is mandatory for therapists.

**The Private Religious Practices Scale:** a 4-item tool that measures the frequency of individual's involvement in religious behaviours: prayer, religious attendance (attending a church or mosque), reading the Bible/Quran, and watching religious programs on television (Fetzer Institute, 2003). The tool uses an ordinal scale and it has acceptable reliability ( $\alpha=0.70$ ). It can be therapist-reported or patient-reported. The tool is not available in Arabic and will be used in its English version (Bodling, et al., 2013).

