**Figure 1: Random generated numbers of intervention group**

## **Box 1: inclusion and exclusion criteria**

Inclusion criteria
▪ Confirmed SCI diagnosis by computed tomography or magnetic resonance report.
▪ ASIA: A, B, and C
▪ Age between 18 and 65 years old.
▪ Stable medical condition.
▪ Time elapsed after SCI is not more than 6 months.
▪ Minimum time of stay in inpatient rehabilitation unit is six weeks.
▪ Active involvement in rehabilitation program.
▪ Sufficient comprehension (read/write) of the Arabic language.
Exclusion criteria
▪ Unconfirmed diagnosis.
▪ Patients who have communication and/or cognitive disorders such as global aphasia and memory deficit.
▪ Patients with disturbed level of awareness such as coma or lethargy.
▪ Time elapsed since SCI is more than 6 months.
▪ ASIA: D and E
▪ Unstable medical condition.
▪ Patients who have other cause(s) of disability in addition to SCI such as stroke or amputation.
▪ Age less than 18 or more than 65 years old.
▪ Time of stay in inpatient rehabilitation unit is less than six weeks.
▪ Inactive involvement in rehabilitation program.
▪ Patients with a progressive disease or a psychiatric condition that would interfere with active participation in rehabilitation program.
▪ Patients with cardiovascular contraindications.
▪ Persons who become walking ambulatory during the inpatient period.
▪ Persons with complete tetraplegia C4 or above.
▪ Persons on mechanical ventilator.

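### The two religiousness scales are put to Arabic-speaking patients by interview from English-only forms, with no fixed Arabic wording for either visit.

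*Combined protocol and SAP*

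**What the plan says.** All of this is in the combined protocol and SAP.

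- **Language of the forms.** Under Data Collection, the paragraphs on the Private Religious Practices Scale and the Organizational Religiousness Short-Form each state "The tool is not available in Arabic and will be used in its English version". The SCIM-III paragraph says the same.
- **Mode.** The same section says "ADL data collection from each participant in the study will take place in a face-to-face interview twice", on admission and 6 weeks later. The list of tools includes "Research assistant-administered SCIM-III, the Private Religiousness Practices Scale, Organizational Religiousness Short-Form".
- **Patients' language.** Box 1 requires "Sufficient comprehension (read/write) of the Arabic language". It asks for no English.
- **Contrast with the SCIM-SR.** "The first author will translate the SCIM-SR to Arabic. The Arabic translation will be piloted in the pilot study".
- **Therapists' language.** The section on the manual requires Arabic of therapists and patients and adds "No other special skills or experience are required". The SCIM-III paragraph says "Good English language comprehension, and the ability to read and write is mandatory for therapists". The therapist-report adherence questionnaire is also to be used in English.
- **Status of the outcomes.** The abstract lists SCIM-III and the two religiousness scales as secondary. The objectives section places them under primary objectives (c and d).

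**The concern.** A patient who need not know English has to be asked English items with ordinal response options. The plan names the form the assistant holds but not the Arabic words the patient hears. Objective d compares the arms on these scales, measured at two interviews. If the phrasing of an item or a frequency option changes between the interviews, part of the recorded change reflects phrasing and not the patient. That widens the spread of change in both arms and makes a real difference harder to see. The plan relies on standardized tools for validity and reliability, and a scale without standard wording in the language of the interview loses part of that property.

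**Working it through.** The plan gives no figure on this point, so the check sets the passages side by side.

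**Step 1: which tools lack an Arabic text.**

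| Tool | Items | Written Arabic version | How administered |
|---|---|---|---|
| SCIM-SR | 17 | Yes, piloted | Completed by the patient |
| SCIM-III | 17 | No | Clinician-rated and observed (objective c); by assessment or interview (tool paragraph); interview (data collection schedule) |
| Private Religious Practices Scale | 4 | No | Research assistant, interview |
| Organizational Religiousness Short-Form | 2 | No | Research assistant, interview |

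**Step 2: where the patient's hearing of the item matters most.** The 4 + 2 = 6 religiousness items ask how often a person prays, attends, reads or watches. The rater can learn this only by asking. The 17 SCIM-III tasks are scored by a rater against criteria on the form and may be observed, so the wording heard matters less there. How much less depends on the mode, which the plan describes in three ways.

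**Step 3: whether anything else fixes the wording.**
- The English requirement in the SCIM-III paragraph secures the reader's understanding of the form, not the patient's. It names therapists, whereas a research assistant administers the tool.
- The remark that the SCIM resists cross-cultural differences supplies no Arabic text and does not concern the religiousness scales.
- The pilot invites comments on unclear items and computes Cronbach's alpha. Alpha describes internal consistency at one sitting and does not measure drift between visits.
- The assistant has a separate session on the data collection tools, but no script, back-translation or same-interviewer rule is described.

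**Step 4: the mechanism.** Suppose, as a simple additive model, that wording contributes a component with variance s² to the score at each visit, with correlation r between a patient's two visits. The variance of the change score then rises by

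s² + s² − 2rs² = 2s²(1 − r).

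If the same words are used both times, r = 1 and the addition is 2s²(1 − 1) = 0. If the two wordings are unrelated, r = 0 and the addition is 2s². The documents give neither s² nor r, so the loss of precision cannot be calculated.

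**Step 5: exposure.** With 90 patients and two visits there are at most 90 × 2 = 180 interviews, at three hospitals. The manual section speaks of one research assistant collecting data; Data Collection also speaks of assessors in the plural. With a single interviewer of steady habit, r would be near 1 and the addition small.

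**The case against.** The best defence is that the documents nowhere say items will be translated aloud on the spot. They name the version of the form and leave open that the team will agree Arabic phrasing in the training session. The pilot uses a well-trained assistant, asks patients and assistant to flag unclear items, and is meant to improve use of the tools. This stands in part. Improvised translation is an inference, and a reader should not conclude that pilot corrections cannot carry into the trial. What remains is that the protocol commits to an English form and gives agreed Arabic wording no written place.

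A reader might extend the point equally to SCIM-III. The documents do not support that: the tool is described as observed and clinician-rated, and a script read verbatim could turn it into a second patient report and undercut objective c.

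A reader might also put a number on the loss by shrinking the quoted alpha of 0.70 to an assumed lower value. Such a figure would rest on a reliability the documents do not give and on a coefficient that does not measure between-visit drift.

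A reader might infer bias between the arms. That would need the blinded assessor to have guessed the allocation, which nothing in the documents shows.

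On therapists' language, the two requirements could refer to different roles: therapists delivering an Arabic manual, and whoever completes SCIM-III. That is a fair reading, but the protocol assigns SCIM-III to a research assistant, and the English adherence form is a therapist report. The statements still need reconciling.

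**Conclusion.** The point holds for the two religiousness scales. They are interview tools, their items must be put to the patient, and the plan specifies English forms with no fixed Arabic wording. The expected consequence is avoidable noise in outcomes that the abstract treats as secondary. Its size is unknown and could be small if one assistant uses the same words throughout. The conclusion assumes that patients are interviewed in Arabic, which follows from Box 1 but is not stated. For SCIM-III, the finding is narrower: the mode of administration is inconsistent, and the need for Arabic prompts depends on how that is resolved. The SCIM-SR is untouched. This is a minor but worthwhile improvement.

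**What to change.** 1. In the Data Collection paragraphs on the two religiousness scales, replace the English-only sentence with a fixed written Arabic version of the six items and their response options. Prepare it alongside the SCIM-SR translation, try it in the planned 15-person pilot, and read it verbatim at both visits. Scores may still be entered on the English form.
2. For SCIM-III, first reconcile objective c, the tool paragraph and the data collection schedule on whether it is observed, assessed or asked by interview. If any items are asked, use agreed written Arabic prompts for those items, while the rater continues to score on the English criteria.
3. Reconcile the language requirements for therapists across the manual section, the SCIM-III paragraph and the adherence questionnaire, naming the role to which each applies.

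The cost is a small amount of translation work before the pilot, and somewhat more if SCIM-III prompts prove necessary. Sample size, outcomes and analysis do not change. The wording should be settled before the first baseline interview, because a later correction would itself change the wording between visits.

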## **Monitoring**

The three researchers will monitor the study on monthly bases during online meetings. Progress, barriers, and action plans will be discussed at each meeting.

## **Data Analysis**

Captured data will be coded and reviewed by the researchers for clarity and completion. A spread sheet will be prepared by the three researchers and then loaded to IBMSPSS 21 for analysis. The first author will perform data entry. The research assistant will check the data entry using the original forms, and the research supervisor will check the data for missing data and entry errors.

The following statistical methods will be used to test the research hypothesis:

- a. To describe participants' characteristics: descriptive statistics such as frequency, percentage, mean with standard deviation for Normally distributed data and median and Inter Quartile range will be used for continuous variables that are not Normally distributed will be used.
- b. Missing values will not be substituted. Intention-to treat analysis method will be used for analysis.
- c. To determine the significance of biographical variables at baseline: McNemar and Chi Square with Nominal variables, T-test and Mann-Whitney for interval variables will be used.
- d. To compare the efficacy of the educational manual: Repeated Measures ANOVA/ Linear Mixed Models will be used will be used to assess differences between intervention and control group using the ADL data. The Repeated Measures ANOVA and Linear Mixed Models will be used to analyze the data. Linear Mixed Models has advantage in dealing with missing values and provides fixed and random effect (Krueger and Tian, 2004).
- e. Adherence to the intervention will be summarized using frequency and percentage.

All the data collected and entered (hardcopy and soft copy) will be securely stored by the first researcher in a locked cabinet on hospital premises (hardcopy) and in a password-protected file online.

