## **Abstract**

**Background:** This study argues that providing evidence-based occupational therapy patient education is vital in order to optimize rehabilitation outcomes. The planned trial aims to evaluate the SADL-eM intervention for people with SCI compared with standard treatment.

**Methods/Design:** This is a parallel randomized clinical trial with two study arms, intervention and control. Ninety patients treated in inpatient rehabilitation settings will be randomly allocated to two study groups. Both groups will receive standard care. The intervention group will also receive a copy of the SADL-eM from their treating occupational therapist during an individual session. Assessment on admission (baseline measure) and after six weeks of admission will use the SCIM-SR as the primary outcome measure. Secondary outcomes include the SCIM-III, Private Religiousness Practices Scale, Organizational Religiousness Short-Form, additional domains of ADL covered by the educational manual and adherence to intervention. Effect will be determined using repeated measures ANOVA.

**Discussion:** The SADL-eM is a comprehensive ADL educational tool that aims to optimize rehabilitation outcomes for people with SCI. If the SADL-eM is demonstrated as clinically effective, this will have significant implications for occupational therapy interventions in LMIC settings.

**Trial registration:** BLINDED FOR REVIEW (Project ID: 1635, HREC Reference number: S17/10/206). Helsinki Committee for Ethical Approval (PHRC/HC/689/20)

**Date of registration:** 30/11/2017, Renewed 12/06/2020

**Keywords:** Occupational therapy, educational intervention, Activities of daily living, Spinal Cord Injury, clinical trials

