### **Ethical Issues**

Ethical approval will be obtained from the BLINDED University Human Research Ethics Committee (HREC). Autonomy of participation or withdrawal, the anonymity of participants, and confidentiality of information collected for research reasons will be assured in the consent form and sustained all through study. The study is unlikely to involve any harm, risk or discomfort to participants. Patients' questions will be answered by the researcher honestly and as fully as possible. Completed questionnaires and signed consents of participants will be

securely stored during and after study completion in a locked cabinet on hospital premises for a period of 5 years after publication. The participants in the control group will receive a copy of the SADL-eM at the end of study with explanation from the researcher.

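### Two efficacy models that treat a missing 6-week score differently are planned under one intention-to-treat label; neither is made primary, and the Abstract names only the one that drops patients without that score

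*Combined protocol and SAP*

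**What the plan says.** Data Analysis, item b, sets the missing-data rule and the analysis principle together: "Missing values will not be substituted. Intention-to treat analysis method will be used for analysis". The intention-to-treat set is not defined further.

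Item d gives the efficacy analysis: "Repeated Measures ANOVA/ Linear Mixed Models will be used will be used to assess differences between intervention and control group using the ADL data". It then says "The Repeated Measures ANOVA and Linear Mixed Models will be used to analyze the data", and adds that "Linear Mixed Models has advantage in dealing with missing values and provides fixed and random effect". It does not say which model carries the conclusion, or what happens if the two disagree.

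The Abstract is narrower: "Effect will be determined using repeated measures ANOVA". The mixed model is not mentioned there.

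Three other places bear on who has a 6-week score:

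- Data Collection fixes two assessments, at admission and six weeks later, and describes measures to limit loss to follow-up without giving an expected rate.
- Ethical Issues assures "Autonomy of participation or withdrawal".
- Box 1 excludes patients who stay under six weeks and patients who become ambulatory during the stay. Both can become known after randomisation, which takes place early in the admission.

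**The concern.** With two visits, the group-by-time test in repeated measures ANOVA is the comparison of mean change between arms, and a patient without a 6-week score has no change. With nothing substituted, that patient leaves the analysis and the baseline score goes too. This is a completers analysis. A mixed model fitted by likelihood to all available scores also substitutes nothing, but it keeps the patient through the baseline score.

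So the two planned models analyse different sets of patients as soon as anyone is lost. Two things are at stake. The reported result may not be what its label says. And with no primary model named, the choice between two differing results could be made after the data are seen.

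**Working it through.** **1. The plan's own figure.** The sample size section gives 90 patients for an effect size of 15%, 80% power and 5% error. I read 15% as Cohen's f = 0.15 and assume a correlation of 0.5 between visits; the plan states neither. For the group-by-time test with two visits, the noncentrality is N × f² × 2 / (1 − 0.5) = 90 × 0.0225 × 2 / 0.5 = 8.1 on 1 and 88 df. Power is 0.804 (0.795 at N = 88). On this reading, 90 is the size for a repeated measures ANOVA with every patient complete, and nothing is added for loss. The same inputs correspond to a difference in change of 0.60 SD, used below as a yardstick.

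**2. Who is analysed.**

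| 6-week score | Repeated measures ANOVA | Linear mixed model |
|---|---|---|
| Present | Included | Included |
| Missing, baseline present | Dropped | Kept through baseline |

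**3. Bias of the completers' change contrast.** Assume equal variances (SD 1), correlation ρ between visits, no true effect, and loss that depends only on baseline. A completer's expected change is then a constant minus (1 − ρ) times the baseline score, so

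bias = (1 − ρ) × (gap in mean baseline between the two arms' completers).

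If the loss pattern is the same in both arms, the gap and the bias are zero.

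**4. Numbers, assuming 15% loss per arm.** Removing the top 15% of a normal distribution shifts the mean of the rest by φ(1.036)/0.85 = 0.274 SD.

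| ρ | Top 15% lost in one arm only: (1 − ρ) × 0.274 | Opposite tails lost in the two arms: doubled |
|---|---|---|
| 0.5 | 0.137 | 0.274 |
| 0.6 | 0.110 | 0.219 |
| 0.7 | 0.082 | 0.164 |
| 0.8 | 0.055 | 0.110 |

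The last column is an upper bound, because it needs clean truncation in opposite directions.

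Softer logistic loss of about 15% per arm, simulated with 2,000,000 patients per arm:

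- Baseline-dependent loss in one arm: 0.071 SD (ρ = 0.5) and 0.040 SD (ρ = 0.7). Scaling to ρ = 0.8 gives 0.071 × 0.2/0.5 = 0.028 SD.
- Opposite directions: 0.138 SD (ρ = 0.5) and 0.081 SD (ρ = 0.7). A separate run gave 0.141 and 0.084.
- Same pattern in both arms: 0.
- Likelihood estimate from all available data: within 0.003 of zero throughout.

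I round the logistic results to 0.03 to 0.15 SD. Against the 0.60 SD yardstick at ρ = 0.5, 0.138 is 0.138/0.60 = 23% and the bound of 0.274 is 46%.

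**5. Trial-sized check.** With 45 per arm, ρ = 0.5, about 20% missing and a true effect of zero (4,000 runs), opposite-direction loss gave a false difference of 0.18 SD for completers and 0.004 SD for the likelihood estimate. With loss completely at random, neither was biased, and the standard errors were 0.234 and 0.227.

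**The case against.** The strongest reply is that the plan already contains the remedy. Item d names the mixed model and gives missing values as its advantage. A reader of the Abstract might infer that patients who withdraw are certain to disappear from the main result. The documents do not support that: it follows only if the ANOVA is the main analysis, which the Data Analysis section leaves open. A reader might also take "Missing values will not be substituted" as contradicting "Intention-to treat analysis method will be used for analysis". It does not, since a likelihood mixed model imputes nothing.

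Second, the bias belongs to the unadjusted change contrast rather than to deletion as such. In the same scenarios, a completers-only analysis adjusted for baseline had bias within 0.001 SD. This stands. The figures describe the ANOVA on change, not every completers analysis.

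Third, harm needs loss that depends on baseline and differs by arm, and the documents contain no evidence of such loss. Retention measures are planned, and eligibility asks for a stay of at least six weeks. On the other side, patients are not blinded, and the named retention incentive, a free copy of the manual, goes to the control arm only. Different reasons to stay are therefore possible, but no more than that.

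Fourth, under loss completely at random the mixed model gains little: 0.227 against 0.234 is a standard error about 3% smaller. This also stands.

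None of these replies settles which model is primary or what the intention-to-treat set is.

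**Conclusion.** The point holds as an unresolved choice with a definite inconsistency between sections. The plan promises intention-to-treat and lists two models that handle a missing 6-week score differently. It ranks neither, and in the Abstract it commits to the one that analyses completers only. If that commitment stands, the intention-to-treat label would be wrong for the main result.

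The possible bias is roughly 0.03 to 0.15 SD under logistic loss and at most 0.27 SD in the opposite-tails case. This rests on an assumed 15% loss and a correlation of 0.5 to 0.8, and on loss that depends on baseline and differs by arm. It is zero if the loss pattern is common to both arms. It would be wrong to conclude that the trial's result will be biased; the documents give no loss rate, correlation or loss pattern.

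The mixed model is not a complete cure. It relies on data being missing at random, and it cannot restore patients removed by a Box 1 criterion met after randomisation. The plan does not say that such patients will be removed, but it does not rule it out. The change is worth making because it costs almost nothing and fixes the choice of model before the data are seen.

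**What to change.** 1. In the Abstract and in Data Analysis item d, name the linear mixed model as the primary SCIM-SR analysis: REML, unstructured covariance over the two visits, with a group-by-visit term. Include all randomised participants with at least one score, in the arm assigned.
2. Make the repeated measures ANOVA on completers a sensitivity analysis.
3. In item b, the sentence on substitution may stay. Add that participants without a 6-week score remain in the model through their baseline score. Report the number missing and the reasons by arm.
4. State that the model assumes data missing at random, and that baseline-only patients add little precision.
5. Add a sensitivity analysis that shifts the unobserved 6-week scores over a stated range in each arm. Each arm's 6-week mean moves by the proportion missing times the shift.
6. Reconcile the intention-to-treat statement with the two Box 1 criteria that can be met after randomisation (stay under six weeks, becoming ambulatory), by saying whether such participants stay in the analysis. Applying those criteria after randomisation would remove patients under either model.

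Cost: wording in two sections and one extra analysis. The shift analysis needs a short imputation or pattern-mixture step. The mixed model is already planned, and no additional patients or outcome measures are needed.
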